Intervention: The intervention will take place in the second half of the study, where the research assistant will inform the provider of the patient's preferred role based on the Patient Preference Scale prior to the clinic visit. The provider will then have a brief conversation at the beginning of the clinic visit where they state "I see that you prefer to have treatment decisions made (*together, by yourself, by me*) today. I appreciate knowing this information." The rest of the encounter will proceed as per the provider's usual practice. All other study procedures will be the same and the same perception scales will be used after the clinic visit and concordance and discordance will be examined as described in the study flow diagram.

Outcomes: The primary outcomes will be role concordance and patient satisfaction with the decision process. Secondary outcomes will be role perception concordance between provider and patient, quality of life at 2 to 6 weeks and 6 months after initial clinic visit, decision regret at 2 to 6 weeks and 6 months after initial clinic visit, and completion or planned completion of recommended therapies at 6 months. These time points were chosen to provide an early assessment of the impact of the intervention and to see if the results are durable after a longer period of time while still allowing us to conclude the study within the funding timeframe. There is evidence that decision regret is stable over time out to 4 years after diagnosis [4]. We will also correlate role

preference and concordance with surgical procedure performed or planned to look for associations between these measures and type of surgery received or planned, controlling for ineligibility for breast conservation.

Risks and Benefits of Participation: Participation is completely voluntary and may be withdrawn at any time. This is a low risk study, but some patients may experience distress from the questions on the surveys. If a patient experiences distress, she will be referred to our in-clinic Licensed Care Social Worker and she will make appropriate referrals to psychiatric care if necessary. There is also a low risk of loss of privacy and patients will be made aware of this. The benefits of participation are greater patient awareness of their own preferences and decisions.

Please see the study flow diagram on the following page.

Record decisions made and intentions
to complete therapy

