Data Management: All surveys will be administered electronically (tablets will be used for in clinic surveys) and stored on a secure University server. The surveys will be collected both in person (when the patient is in clinic) and electronically. The surveys will be built into and collected in the Research Subject Registry (RSR) database. Only study personnel will have access to the data and the PI will be responsible for deciding the role and level of access for each person. All digital audio recordings will be stored on a secure, password protected University computer in a locked office at Huntsman Cancer Institute. Again, only study personnel will have access to this data. The digital recordings will be transcribed and de-identified for coding and analysis. The de-identified transcripts will only be available to trained coders, the PI, and study coordinator. The electronic transcriptions will be stored on University based, password protected computers in the secured office area of the PI. Badge access is required to enter the office area during non-business hours. Paper versions will only be used if necessary due to computer outages or significant feasibility issues with the electronic transcripts and will be stored in a locked filing cabinet in the PIs locked office. Again, access will only be given to study personnel.

Statistical Analysis:

We are interested in evaluating whether patients play their desired role in treatment planning, and whether informing providers of patients' preferred roles improves patients' perception of achieving their desired role. Specifically, we will study two groups of patients, a non-intervention control group, where providers are blind to the patient's preferred decision making role and an intervention group where the provider is informed of the patient's preferred role. For this study we plan to enroll 100 patients, where the first 50 will be in the no intervention group and the next 50 will be in the intervention group. We expect the results to provide preliminary data for powering a larger extramural grant.

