The primary aim of our study (a) is to evaluate patient perception of whether the patient achieved his/her preferred role in the treatment decision. This aim will be met by estimating perception concordance between baseline and after the clinic visit within the intervention and control groups, and testing for group differences in concordance. A secondary goal (b) will be to similarly estimate concordance of provider's perception of the patient's preferred role versus the patient's perception of the achieved role (where both scales will be measured after the clinic visit). In addition, we also plan to test the following outcomes between groups: c) patient's satisfaction with the decision making process, d) FACT-B assessment of short-term QOL, e) decision regret, f) OPTION assessment of patient involvement and g) completion or intention to complete therapies. Finally, we will compare the patient role concordance estimated in a) with improved short-term and longer-term improvements in: outcomes c)-g). Specific methods corresponding to each analysis objective are described below.

a-b) Concordance measures. The patient and provider perception scales consist of 5 levels ranging from active to passive involvement in treatment decisions. Consistent with other similar studies [5-7], our primary concordance measure will be defined as exact agreement in patient responses between the baseline and post clinic visit. Within each group we will provide concordance rates and the associated 95% confidence interval (CI) using the Wilson Score interval approach. We will also report the weighted Kappa coefficient and its 95% CI. Group differences in concordance will be tested using a chi-squared or Fisher's exact test. As a sensitivity analysis for this assessment, we may adjust for potential confounders in a logistic framework predicting concordance. We will consider the following variables for adjustment if they are associated with the concordance outcome: age, education level, and stage of disease.

c) Patient's satisfaction with the decision making process. Satisfaction with the decision making process will be measured directly after the clinic encounter using a modified version of the Holmes-Rovner Satisfaction with

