Patient Perception Scale	Role the patient perceives they played in decision making process		X		
Provider Perception Scale	Role the provider perceives the patient played in the decision making process		X		
FACT-B	Breast cancer specific health related quality of life	X		X	X
Decision Process Satisfaction Scale	Level of satisfaction patient had with the decision making process		X		
Decision Regret Scale	Regret about decision made			X	X
OPTION Scale	3rd party assessment of patient involvement in decision making (from recorded encounter)		X		

Sample Size Justification

Concordance estimates. A similar study conducted by Bilodeau and Degner estimated 50% agreement between a patient's initial decision-role preference and the role that was achieved [13]. Within each group (n=50), we expect to achieve a confidence interval (CI) width of 29% for an expected concordance of 50%, corresponding to a 95% CI of 36%-64%.

Comparison of intervention versus control concordance. With 50 subjects per group we would have 80% power to detect an absolute increase in concordance of 28% in the intervention versus the control group using a two-sided Fisher's exact test at a 0.05 significance level.

Selected References

1. Hack, T.F., et al., *Behind closed doors: systematic analysis of breast cancer consultation communication and predictors of satisfaction with communication.* Psychooncology, 2010. **19**(6): p. 626-36.
2. Clayton, M.F., et al., *Assessing patient-centered communication in a family practice setting: how do we measure it, and whose opinion matters?* Patient Educ Couns, 2011. **84**(3): p. 294-302.
3. Hack, T.F., et al., *Promoting consultation recording practice in oncology: identification of critical implementation factors and determination of patient benefit.* Psychooncology, 2013. **22**(6): p. 1273-82.
4. Martinez, K.A., et al., *Decision Regret following Treatment for Localized Breast Cancer: Is Regret Stable Over Time?* Med Decis Making, 2015. **35**(4): p. 446-57.
5. Lantz, P.M., et al., *Satisfaction with surgery outcomes and the decision process in a population-based sample of women with breast cancer.* Health Serv Res, 2005. **40**(3): p. 745-67.
6. Janz, N.K., et al., *Patient-physician concordance: preferences, perceptions, and factors influencing the breast cancer surgical decision.* J Clin Oncol, 2004. **22**(15): p. 3091-8.

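### Does leaving the primary concordance test as chi-squared or Fisher's exact make the result depend on a choice made after the data are seen?

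*Combined protocol and SAP*

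**What the plan says.** Under Outcomes, "The primary outcomes will be role concordance and patient satisfaction with the decision process". Concordance is binary: the patient's preferred and achieved roles either match exactly or do not. Under Statistical Analysis, a-b) Concordance measures, two things are planned for it. The first is descriptive: "Within each group we will provide concordance rates and the associated 95% confidence interval (CI) using the Wilson Score interval approach". The second is the comparison: "Group differences in concordance will be tested using a chi-squared or Fisher's exact test". Neither sentence says whether a continuity correction applies, and the second does not say what decides between the two tests. Item g), on completion of therapies, uses the same either-or wording.

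Sample Size Justification is more specific about the same comparison: "With 50 subjects per group we would have 80% power to detect an absolute increase in concordance of 28" percentage points, "using a two-sided Fisher's exact test at a 0.05 significance level". The control rate comes from a cited study that "estimated 50% agreement between a patient's initial decision-role preference and the role that was achieved". On allocation, "the first 50 will be in the no intervention group and the next 50 will be in the intervention group". On purpose, the Statistical Analysis section says: "We expect the results to provide preliminary data for powering a larger extramural grant".

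**The concern.** A primary analysis should be fixed before the data are seen. Here two tests are named for a primary outcome, and with 50 per group they do not always agree. Uncorrected chi-squared is the more liberal of the two, so an open choice can only move a borderline result towards significance. The two available clues also point different ways. The common convention (chi-squared unless expected counts are small) would select chi-squared at the concordance rates expected here, while the power statement uses Fisher's. If the choice often changed the conclusion, or pushed the false-positive rate well above 5%, the text would need to be tightened.

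**Working it through.** **Inputs.** 50 patients per group and control concordance of 50% (25/50); two-sided 0.05; design difference 28 points, so 50% versus 78%. All come from Statistical Analysis and Sample Size Justification. The expected-count convention is an assumption, since the documents do not state it.

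**1. The plan's power figure.** Sum the binomial probabilities of all 51 × 51 = 2,601 possible outcomes, counting those with p ≤ 0.05:

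| Test | Power, 50% vs 78% | Difference detectable with 80% power |
|---|---|---|
| Fisher's exact | 78.9% | 28.3 points |
| Chi-squared, uncorrected | 84.3% | 26.6 points |
| Chi-squared, continuity-corrected | 78.9% | 28.3 points |

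The stated 80% for 28 points is reproduced, to rounding, with Fisher's test.

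**2. A borderline table: 25/50 versus 35/50.**
- Uncorrected: χ² = N(ad − bc)² / (product of the four margins) = 100 × (25×15 − 25×35)² / (50×50×60×40) = 100 × 500² / 6,000,000 = 4.17, p = 0.041.
- Continuity-corrected: 100 × (500 − 50)² / 6,000,000 = 3.375, p = 0.066.
- Fisher's exact: p = 0.066.
- Expected counts: 50×60/100 = 30 and 50×40/100 = 20. At 25/50 versus 39/50 they are 50×64/100 = 32 and 50×36/100 = 18. None is small, so the convention selects chi-squared.

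**3. How wide the split is.** From a control count of 25/50:

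| Intervention | Uncorrected χ² p | Fisher's p |
|---|---|---|
| 34/50 (+18 points) | 0.067 | 0.103 |
| 35/50 (+20 points) | 0.041 | 0.066 |
| 36/50 (+22 points) | 0.024 | 0.040 |

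Among improvements from 25/50, only 35/50 separates the tests. An observed gain of exactly 20 points separates them for control counts 11/50 to 29/50 (χ² p 0.032 to 0.046; Fisher's 0.053 to 0.071). At 10/50 and 30/50 both are significant (0.029 and 0.049).

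**4. How often they disagree, with true control concordance 50%.**

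| True gain | Probability of disagreement |
|---|---|
| 0 points | 2.2% |
| 10 points | 5.0% |
| 20 points | 8.2% |
| 28 points | 5.4% |

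**5. The cost of choosing after the fact.** Across all 2,601 tables there is none where Fisher's gives p ≤ 0.05 and uncorrected chi-squared does not. Choosing the more favourable test therefore rejects exactly when uncorrected chi-squared does. At a common rate of 50% that is 5.7%; Fisher's alone rejects 3.5%. The gap, 5.69% − 3.52% = 2.17%, is the disagreement rate in step 4. The excess over nominal is 5.7% − 5% = 0.7 points.

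**6. If chi-squared means the corrected form.** Continuity-corrected chi-squared and Fisher's give the same decision at 0.05 in all 2,601 tables, so the choice has no effect.

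**7. The group intervals.** At 25/50 the Wilson interval is 36.6% to 63.4% uncorrected (width 26.7 points) and 35.7% to 64.3% corrected (width 28.6). The stated 36% to 64% and 29% match the corrected form. They also match an exact Clopper-Pearson interval (35.5% to 64.5%, width 28.9), so they do not show which Wilson form was intended. The difference is about 2 points of width and alters no between-group result.

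**The case for a change.** The strongest case for a change is that this is a primary outcome, the text is open, and any disagreement runs in one direction only. Naming a test would take one sentence and need no data. The expected-count convention does not rescue the wording, because it leads to chi-squared while the power statement describes Fisher's. The plan also has no interval for the difference in concordance, which would help in planning the larger study. For 25/50 versus 35/50, a Newcombe interval is +0.8 to +37.2 points uncorrected and −0.6 to +38.5 points corrected, so the unstated Wilson form would carry through to it.

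The facts in this stand: no rule is written, and the two clues differ. The inference that the primary result is at risk does not. The same nesting that makes the choice one-directional also caps the harm at the error rate of a standard test. Fixing Fisher's is a trade rather than a pure gain: 84.3% − 78.9% = 5.4 points of power at the design difference, for a test that rejects only 3.5% of the time under no difference at 50%. An interval for the difference would be a useful reporting addition, but the plan does not propose one, so the behaviour of its two forms is not an error in what is planned. The two group rates, which a later power calculation would use, do not depend on the test.

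**Conclusion.** No change is needed. The wording leaves a gap that a competent analyst fills sensibly, with either of two accepted tests. The largest consequence found is a false-positive rate of 5.7% instead of 5% at a common concordance rate of 50%, and none beyond Fisher's own if chi-squared is continuity-corrected. Conclusions differ only for borderline results: 2.2% of the time with no true difference, and 8.2% at a true 20-point gain. The sample size is unaffected, and the stated power is reproduced with the test it names.

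This rests on 50 analysable patients per group and, for the probabilities, on the plan's 50% control rate. It also weighs the study's stated role as preliminary work for a larger grant, where the estimated rates matter more than which side of 0.05 one p-value falls.

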**An Intervention to Improve Decision Role Concordance
amongst Newly Diagnosed Breast Cancer Patients**

Study Protocol and Statistical Analysis Plan

The University of Utah IRB #:

00081898

May 17, 2016

Project Summary: Role concordance among patients and providers during the decision making process can impact outcomes, but there is a lack of interventional studies in the literature aimed at improving role concordance during treatment decision making for breast cancer patients. The proposed design is a mixed methods, interventional study with concurrent controls to examine the effects of an intervention to improve role concordance on decisional outcomes and breast cancer specific quality of life among newly diagnosed breast cancer patients.

Project Description:

Rationale: This study is innovative because it is an interventional study aimed at improving role concordance in the treatment decision making process for newly diagnosed breast cancer patients. There are currently no standards of care for patient centeredness in clinical decision making. This project will provide a foundation for a research program that will change this, focusing on treatment decision making in breast cancer patients.

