Overview: The proposed design is a mixed methods, interventional study with concurrent controls to examine the effects of an intervention to improve role concordance on decisional outcomes among newly diagnosed breast cancer patients. Providers will be blind to the patient's preferred decision making role in the first half of the study and then informed of the preferred role in the second half of the study. The intervention will be a short conversation that providers will have with patients at the beginning of the clinic visit where the provider identifies the patient's preferred role and their desire to help the patient achieve it. Quantitative comparisons before and after implementation of the intervention and qualitative analyses of the recorded clinical encounters will be performed to evaluate the effects of the provider directed behavioral intervention to improve role concordance. This study design was chosen because once the intervention is introduced providers may have difficulty omitting this behavior from the clinical encounter and this could confound our results. If patient-level randomization was used, providers would need much more oversight and coaching in order to not "forget" which patient is in which arm and the study effects may be biased toward the null. In this small study, if provider-level randomization was used, this could significantly bias assessments of patient involvement due to inherent differences in how the providers approach clinical interactions at baseline. Also, we do not anticipate substantial variability in the pre and post populations during the short time period of the study other than the date of their consultation and, thus, we expect that the populations will be very similar in other characteristics. We plan to examine differences between pre and post-intervention patients to evaluate this.

Objectives:

1. Investigate the impact of a brief provider-led intervention about the patients' preferred role in treatment decision making on role concordance. **We hypothesize that:**
 - a. Role concordance will be improved when the preferred role is discussed with the patient at the beginning of the encounter.
 - b. The provider's perception of the role achieved will be more concordant with the patient's perception when the preferred role is discussed.

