2. Investigate the impact of role concordance in the treatment decision making process on short term and long term quality of life and decision outcomes. **We hypothesize that:**
 - a. Patients who achieve role concordance will be more satisfied with the decision process.
 - b. Patients who achieve role concordance will have better QOL and less decision regret at early (2 to 6 weeks) and later (6 months) timepoints after the clinic visit.
 - c. Patients who achieve concordance will be more likely to complete or plan to complete recommended treatments.

Study Subjects: The study population will be newly diagnosed female breast cancer patients scheduled to see one of four breast surgeons at the Huntsman Cancer Hospital Breast Surgery Clinic at the University of Utah. We will exclude patients who have had breast cancer previously, cannot read or write, or have a primary language other than English.

Recruitment: All newly diagnosed patients scheduled in our clinic will be given a recruitment letter as part of their new patient materials (sent the day they scheduled their appointment). They will then be called the day before their visit to gauge interest in participation. If they express interest, they will be sent a consent form electronically so that they can familiarize themselves with the study. They will be asked to arrive at least 30 minutes early for their scheduled appointment (most patients do this anyway) and will be met by a research assistant who will explain the study again and obtain written consent. This same assistant will administer the study scales before and after the clinic visit. Providers will not consent patients nor administer any patient assessments for the study because they will also be delivering the intervention. We expect to enroll a total of 100 patients with 50 in the first year and 50 in the second. We see over 400 new breast cancer patients per year and therefore need approximately 12% of these patients per year to participate in order to reach our recruitment goals. Prior studies using similar methods have had excellent enrollment rates with 98% of eligible patients interested in enrollment.

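### The controls are labelled concurrent although allocation is sequential, and no planned analysis accounts for surgeon if the surgeon mix differs between the two phases

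*Combined protocol and SAP*

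**What the plan says.** **Design label.** The label appears twice. The Project Summary has "interventional study with concurrent controls to examine the effects of an intervention to improve role concordance on decisional outcomes and breast cancer specific"; the Overview repeats it in shorter form as "mixed methods, interventional study with concurrent controls".

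**Actual allocation.** Methodology, Intervention and Statistical Analysis all put the first 50 patients in the control group and the following 50 in the intervention group. Recruitment expects "50 in the first year and 50 in the second". The Overview also speaks of two halves of the study and of before/after comparisons.

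**Surgeons.** Patients are "scheduled to see one of four breast surgeons". In rejecting provider-level randomization, the Overview says "this could significantly bias assessments of patient involvement due to inherent differences in how the providers approach clinical interactions at baseline".

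**Comparability of the phases.** The Overview states "we do not anticipate substantial variability in the pre and post populations during the short time period of the study" and adds "We plan to examine differences between pre and post-intervention patients to evaluate this". It names no variables for this comparison and ties no analysis to its result.

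**Adjustment.** The group comparison of concordance is an unadjusted chi-squared or Fisher test. An optional logistic sensitivity analysis follows: "We will consider the following variables for adjustment if they are associated with the concordance outcome: age, education level, and stage of disease". Section c) extends the list with treatment variables (surgery type, sequencing, complications, chemotherapy and radiation recommendations). Sections d), f) and g) reuse that list, and e) follows d). Surgeon is not a covariate, stratum or random effect in any of them.

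**The concern.** There are two separate points.

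**Label.** No control patient is treated in the same period as an intervention patient. Calling the controls concurrent suggests that change over calendar time is controlled, and it is not.

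**Surgeon.** The plan names provider differences as a source of bias and then leaves surgeon out of every model. Its warning concerns patient involvement, so it bears most directly on OPTION (f). Carrying it over to role concordance (a) and satisfaction (c) is an inference. For b) the route is more direct: the surgeon completes one of the two scales being compared, so rating habits can enter the outcome.

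The bias needs two conditions: surgeons who differ, and shares that change between phases. If both occur, the crude comparison mixes case-mix change with intervention effect, and it can create a difference or hide one. Statistical Analysis says the results will help power a larger grant, so a distorted difference would carry into that calculation.

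**Working it through.** **The plan's own figure.** Sample Size Justification gives 80% power for a 28-point increase, with 50 per group and a two-sided Fisher test at 0.05. Taking 50% versus 78% and enumerating all 51 × 51 outcomes gives 78.9% (uncorrected chi-squared 84.3%). The figure reproduces. With no effect and a stable mix, the actual level is 3.5% for Fisher and 5.7% for chi-squared.

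**Assumed inputs (the documents give none of these).**
- Surgeon concordance rates: narrow 40/47/53/60%, or wide 30/45/55/70%.
- Mix by phase: mild shift from 25% each to 15/20/30/35%, or large shift from 40/30/20/10% to 10/20/30/40%.
- No intervention effect.

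**Bias formula.** Spurious difference = sum over surgeons of rate × change in share.
- Large/wide: phase 1 = 0.40×0.30 + 0.30×0.45 + 0.20×0.55 + 0.10×0.70 = 0.435. Phase 2 = 0.10×0.30 + 0.20×0.45 + 0.30×0.55 + 0.40×0.70 = 0.565. Difference 0.130.
- Mild/wide: 0.545 − 0.500 = 0.045.
- Large/narrow: 0.3×(0.60 − 0.40) + 0.1×(0.53 − 0.47) = 0.066.
- Mild/narrow: 0.523 − 0.500 = 0.023.

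These are worst cases, in which the shares move steadily towards the surgeons with higher rates. The average is over all 24 ways of matching surgeons to shares, using the absolute bias.

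**Concordance, type I error of the crude tests (exact enumeration).**

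| Scenario | Worst-case bias (points) | Worst-case Fisher | Average bias (points) | Average Fisher | Average chi-squared |
|---|---|---|---|---|---|
| Mild/narrow | 2.3 | 4.0% | 1.2 | 3.7% | 5.9% |
| Mild/wide | 4.5 | 5.4% | 2.3 | 4.2% | 6.6% |
| Large/narrow | 6.6 | 7.7% | 3.3 | 4.9% | 7.5% |
| Large/wide | 13.0 | 21% | 6.7 | 9.2% | 12.9% |

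A surgeon-stratified Mantel-Haenszel test (simulated, no continuity correction) stays at 4.9–5.0% throughout.

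**Satisfaction.** Assume a within-surgeon SD of 1 and surgeon means of −0.2/−0.07/0.07/0.2 (narrow) or −0.4/−0.13/0.13/0.4 (wide). The same formula gives, for large/wide, 0.3×0.8 + 0.1×0.26 = 0.27 SD.

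| Scenario | Worst-case bias (SD) | Worst-case t-test error | Average t-test error |
|---|---|---|---|
| Mild/narrow | 0.05 | 5.7% | 5.2% |
| Mild/wide | 0.09 | 7.2% | 5.8% |
| Large/narrow | 0.13 | 10.0% | 6.6% |
| Large/wide | 0.27 | 24.6% | 11.4% |

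A linear model with group and surgeon holds 4.9–5.0%.

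**Period effect.** Assume instead a stable mix and a 10-point rise in every surgeon's rate, from a base of 50%, with no intervention effect. Fisher rejects in 13%, chi-squared in 18% and the stratified test in 17–18%. Surgeon adjustment does nothing for calendar drift.

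**The case against.** **The label is editorial.** The sequence is stated openly in several sections, and the Overview explains why it was chosen. Period confounding belongs to that design, and no analysis change removes it. This stands, so the label is a wording correction.

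**The surgeon bias is hypothetical.** The documents give no between-surgeon differences and no expected shift, and one pool of four surgeons is meant to serve both phases. This also stands. With patients arriving from a stable 25% mix, chance imbalance gives a bias with SD of √(2 × 0.02125/50) = 2.9 points for the wide rates and √(2 × 0.00545/50) = 1.5 for the narrow, and the planned tests keep their level. The 21% figure combines the largest shift, the widest spread and the worst alignment. The chi-squared averages should be read against that test's 5.7% with no shift.

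**Existing protection.** The pre/post comparison could include surgeon, and an adjusted model already exists. But the comparison does not name surgeon and triggers nothing. The model is optional, screens covariates on association with the outcome, and omits surgeon. Nothing fixes surgeon shares by phase, so even an obvious imbalance would be handled only post hoc.

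These arguments limit the weight of the point. They do not show that surgeon is handled anywhere.

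**Conclusion.** Both points hold. The concurrent label contradicts the allocation rule and overstates the design. Surgeon is missing from every analysis, although the plan itself names provider differences as a source of bias.

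The size of the surgeon bias is unknown. On the assumed ranges it is negligible to modest for mild shifts, and material only when a large shift meets wide surgeon differences. If the mix is stable, the planned tests are unaffected. The stated power is not in question. The change is worth making because it is cheap and because an adjustment chosen after seeing an imbalance is less credible. Should fix, with medium confidence.

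**What to change.** 1. In the Project Summary and Overview, replace the concurrent label with sequential (before/after) controls. State that period effects cannot be separated from the intervention effect, and that surgeon adjustment does not cure this.
2. Report each surgeon's patient count by phase within the planned pre/post comparison.
3. Keep the chi-squared/Fisher test as the planned test. Beside it, make one sensitivity analysis mandatory for a) and b): surgeon-stratified Cochran-Mantel-Haenszel with the stratified risk difference and 95% CI, or logistic regression on group and surgeon. Do not screen surgeon on association with the outcome.
4. Keep the t-tests for satisfaction (co-primary under Outcomes) and OPTION, and add surgeon as a prespecified term in their linear models.

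**Feasibility of the logistic option for a).** At 50% versus 78%, discordant patients number 25 + 11 = 36. With four parameters (group plus three for surgeon), 36/4 = 9 events per parameter, within the 5–10 guide that the plan states for g). The documents give no rate for b), so the stratified test is the safer choice there.

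**Cost.** SAP wording, one table and three degrees of freedom. The treating surgeon is known for every patient. The planned tests keep their stated power; the added analyses lose some power only if the mix shifts strongly:
- At the plan's 28 points, added to every surgeon's rate, stratified power averages 87%/84% (wide/narrow) with a stable mix, 86%/83% with a mild shift and 79%/75% with a large shift. The wide figures are flattered because one surgeon's rate reaches 98%.
- At an assumed 25 points, the corresponding figures are 77%/74%, 76%/73% and 68%/65%, against 67.5% for Fisher and 74.5% for chi-squared with no shift.
- For satisfaction at an assumed 0.57 SD, the surgeon-adjusted model has 79%, 78% and 70% power, against 77–80% for the t-test with no shift.
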